- Programmers will identify eligible patients based on the presence at least 1 of the
- cardiovascular conditions listed in **Table 1** and with a prescription for at least 1 of the classes
- of medications to treat the cardiovascular conditions listed in **Table 1**. Participants must be
- patients at UCHealth, Denver Health, and the VA. Patients must have had a fill for a
- medication of interest within the 100 days prior to the cohort build date.
- 150 There will be minimal exclusions criteria: 1) patients who have neither a landline or cellphone;
- or 2) enrolled in hospice or palliative care; or 3) Non-English or Spanish speaking; 4) residing
- out of the state of Colorado.

144

159

- Patients with a refill gap of at least 7 days within the past year utilizing pharmacy refill data will
- be eligible to receive nudges. We will specifically target patients from the following patient
- groups: 1) Age > and <= 65 years of age; 2) Male and female patients; 3) one versus multiple
- cardiovascular condition of interest; and 4) English and Spanish speaking patients.
- 157 **Table 1**. Inclusion criteria for the study based on cardiovascular conditions and medications classes of interest

Condition	Classes of medications
Hypertension	Beta-blockers (B-blockers), Calcium Channel Blocker (CCB), Angiotensin converting enzyme inihibitors (ACEi), Angiotensin Receptor Blockers (ARB), Thiazide diuretic
Hyperlipidemia	HMG CoA reductase inhibitor (Statins)
Diabetes	Alpha-glucosidase inhibitors, Biguanides, DPP-4 inhibitors, Sodium glucose transport inhibitor, Meglitinides, Sulfonylureas, Thiazolidinediones, and statins
Coronary artery disease	PGY-2 inhibitor (Clopidogrel, Ticagrelor, Prasugrel, Ticlopidine), B-blockers, ACEi or ARB and statins
Atrial fibrillation	Direct oral anticoagulants, B-blockers, CCB

Opt-out Consent Process

- Programmers will develop identical study databases within each HCS to store potential
- participants. All data will be stored on secure, separate servers or on RedCap.
- We will use this pool to send opt-out consent letters to potential participants. An opt-out
- 163 consent packet will be sent to all eligible patients prior to randomization. The packet will
- 164 contain an introductory letter with information about the study, an opt-out form, and a self-
- addressed, stamped envelope. An opt-out survey will also be included. This opt-out survey
- aims to gauge the reason for patients opting-out. The survey is optional.

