Available sample sizes: We obtained data from each of the three health care systems on the number of patients at the eight specific clinics (VA, 2 clinics; UCHealth, 4 clinics; DH, 2 clinics) to be included in this study. Figure 1 below shows estimated numbers of patients seen, numbers with CVD conditions and prescribed CVD medications, and numbers with 7 day gap. These patients will be invited to participate, and assuming 80% agree to participate, and 90% of those yield usable outcome data, we expect to have usable outcome data for about 4,364 patients, or about 1,091 per treatment arm. Thus, we expect to have ample subjects (about seven times as many as needed) to achieve the necessary power for the primary analysis of PDC. Additional subjects will provide power for secondary analyses, and for analyses of secondary outcomes.

Exploratory

Covid Messaging

On April 6, 2020, the Nudge Study started to send Covid messages to patients enrolled in the study (Amendment PAM006-1, approved March 18, 2020).

This study plans to scale the concept of the Nudge Study to other applications in the future. We propose pulling data regarding Covid testing of patients sent messages after April 6, 2020 to compare with Arm 1 (non interventional arm).

Comparing opt out vs opt in demographics

There is a growing interest in learning more about who is opting out of our study, as well as who is opting in.

Our study plans to compare the demographics of patients (race, age, ethnicity, gender) that have opted in vs opted out of our study. This requires pulling data from Electronic Health records to compare both cohorts.

We propose (12/1/20) to retrospectively pull demographic data from the EHR for patients that have opted out of the study (race, age, ethnicity, gender) to compare these data with patients that have opted in to the Nudge study. Moving forward, we will include a statement in the opt out packet (**Information Sheet**, v 12/1/20) to inform potentially-eligible patients that receive an opt out packet that demographic information will be drawn.

Qualitative Analysis

Assessment of patient perspectives

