Longitudinal models and GEE: To account for the situations of shortened PDC observation and possible resulting biases we will use a longitudinal model with PDC calculated for monthly intervals. We will use GEE with identity link and independence with unequal variances for the covariance structure. This approach provides robust and likely conservative (Hernán et al., 2002) estimation using empirical (sandwich) variance estimates, but is valid only for MCAR data. However, use of weighting can extend GEE to data missing at random (MAR). In this approach, observation-specific weights are equal to the inverse probability that the longitudinal value was observed. Probability of observation will be estimated by a logistic regression model for whether the value was observed (y/n), with covariates listed in section 3.1.c below. Weights greater than the 95th percentile of weights will be set to the 95th percentile weight. These methods can be implemented for example in SAS PROC GEE (Lin & Rodriguez, 2015) or R package wgeesel (Xu et al., 2018). We will use multiple imputation to impute missing covariate data. We will carry out the recommended sensitivity analyses to the MAR assumption using methods based on pattern mixture models and imputation, by assuming a range of

perturbations of imputed values and assessing differences in model conclusions (e.g. White et al., 2011; Fiero et al., 2017).

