Composite PDC with differing lengths of follow-up: In general, PDC is the sum of observation days covered divided by the sum of observation days. Due to variations from the planned 365 days of assessment, there are several ways of calculating composite PDC for multiple medications. Information on hospitalizations, and on medication changes and cancellations, will be available from the patient's electronic health record. Note that at-risk days is medication specific, as medications may change during the one-year assessment period. Our primary PDC calculation will be PDC-C1 = (sum of numerators of medication-specific PDCs) / (sum of denominators of medication-specific PDCs). This can also be viewed as a weighted sum of medication-specific PDCs with weights equal to the proportion of the 365 target days for which PDC was observed, and equally weights each day on each medication. PDC-C1 will be the outcome definition in the longitudinal models described in section 3.1.a. As a sensitivity

analysis we will also consider an alternate definition, PDC-C2 = average of medication-specific PDCs, which equally weights medications regardless of their length of observation. When all medications are observed for 365 days these definitions are equal. For the longitudinal analyses planned, these definitions will be applied within each longitudinal interval. We will carry out the recommended sensitivity analyses based on pattern mixture models, by assuming various values for difference in means between observed and unobserved data and assessing differences in model conclusions.

3.1.c Adjustment/propensity covariates

The linear weighted GEE model for PDC and the logistic model for propensity of observation will each contain terms for randomization stratification variables health care system (VA, Denver Health or CUHealth), number of CV medications prescribed at baseline (1-2 or 3+), calendar month of randomization; treatment arm, follow-up month from randomization in longitudinal analysis, and treatment by follow-up month interaction; patient demographics age, race, ethnicity, insurance status, and marital status; and comorbidity variables hypertension, hyperlipidemia, coronary artery disease, diabetes, atrial fibrillation, chronic heart failure, chronic kidney disease, cerebrovascular disease, prior myocardial infarction, prior revascularization, depression, PTSD, and substance abuse.

3.1.d Alternate measures of medication adherence

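### The closed covariate list in SAP 3.1.c leaves out sex, which the EHR holds; adding it, and pre-randomization language where usable, is a small improvement at little cost

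*Combined protocol and SAP*

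**What the plan says.** SAP 3.1.c states that "The linear weighted GEE model for PDC and the logistic model for propensity of observation will each contain terms for" a named set of covariates: design variables, treatment arm, follow-up month and their interaction, demographics, and thirteen comorbidities. The demographics are "patient demographics age, race, ethnicity, insurance status, and marital status". Nothing in the section allows further terms. SAP 3.1.a ties the weights to the same list: "Probability of observation will be estimated by a logistic regression model for whether the value was observed (y/n), with covariates listed in section 3.1.c". The summary of revision names the detailed specification of covariates as one of the main changes, so the list is meant to be final.

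The protocol's Inclusion & Exclusion Criteria name four pairs of groups to target, among them "Male and female patients" and "English and Spanish speaking patients". Under the exploratory comparison of opt-outs, the study plans to "compare the demographics of patients (race, age, ethnicity, gender") using EHR data. Language appears as an exclusion criterion. Under the opt-out consent process it also sets the language of the mailed packet at UCHealth and Denver Health, for patients who had already stated a preference. VA materials go out in English only.

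**The concern.** An analyst who follows 3.1.c as written will adjust for marital status and PTSD but not for sex. Of the four targeted pairs, age has a term and the qualifying conditions enter as comorbidities; sex and language have none.

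Two things are at stake. The first is precision: a baseline variable related to PDC is left unused. The second is the missing-data assumption. SAP 3.1.a says that unweighted GEE is valid only under MCAR and uses weights to extend it to MAR. It also accepts that early termination, apart from the VA and UCHealth disruptions, is probably not MCAR. MAR is then claimed conditional on the listed covariates, and it is easier to defend if sex, and language where known, are among them.

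**Working it through.** **The plan's own figure.** SAP 3.1.f: difference 0.10, SD 0.22, two-sided alpha 0.05/6, power 80%. The normal approximation is n = 2 x (0.22/0.10)^2 x (2.638 + 0.842)^2 = 117.2, so 118 per arm; the two-sample t-test gives 118.97, so 119, as stated. The point does not depend on this figure.

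**Availability.**

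| | Sex | Language |
|---|---|---|
| Named as an EHR demographic | Yes, as gender | No |
| Known before randomization | Yes | Only if a preference was already stated |
| Usable at the VA | Yes | Little variation expected |
| Can change after randomization through the intervention | No | Yes: Spanish can be requested by text, and usual care receives no texts |

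**Precision.** Enrollment is 1,235 + 7,266 + 1,000 = 9,501, about 2,375 per arm.
- SE of an arm difference = 0.22 x sqrt(2/2,375) = 0.00638. This ignores the weights and the covariates already listed.
- Detectable difference at the stage 1 level 0.05/3 with 80% power = (2.394 + 0.842) x 0.00638 = 0.0207, about 2.07 points.
- SE ratio = sqrt(1 - added R2). For 0.5% it is 0.9975 and for 2% it is 0.990. The detectable difference becomes 2.06 and 2.04 points.
- At an added R2 of 5%, an outer assumption, the ratio is 0.975 and the detectable difference 2.01 points.

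**Chance imbalance.** Assume a group share p of 20-50% and a PDC gap of 5 points. A 1.96-SD imbalance moves an arm difference by 1.96 x sqrt(2p(1-p)/2,375) x 5 points, which is 0.11-0.14 points. This is random error, not bias.

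**Differential observation at month 12.** Assumptions, none from the documents: PDC gap 5 points; 85% observed; group share p of 20-50%; observation 5-10 points lower for that group in the texted arms only. The group's share among those observed in a texted arm is p x o1 / (p x o1 + (1-p) x o0).
- p = 0.2, 5 points lower: 0.2 x 0.80 / (0.16 + 0.68) = 0.1905. The shift is 0.0095, and 0.0095 x 5 = 0.05 points.
- p = 0.5, 10 points lower: 0.5 x 0.75 / (0.375 + 0.425) = 0.46875. The shift is 0.03125, and 0.03125 x 5 = 0.16 points.
- If observation is equally lower in every arm, the shares match and the bias in the contrast is zero.

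**Does a main effect in the weight model repair this?** I fitted the weight model with arm and group main effects to the same scenarios. At p = 0.2 with 5 points lower, the weighted group shares are 0.207 in control and 0.198 in the texted arms, leaving 0.05 points. At p = 0.5 with 10 points lower they are 0.518 and 0.493, leaving 0.13 points. The pooled coefficient reweights control as well, so the gap between arms largely remains. A term in the outcome model does remove it when the group's effect on PDC is additive.

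**The case against.** The best defence is that little turns on this. The protocol's modeling section says covariates are chosen in advance on clinical grounds and data quality, and the sentence on target groups concerns breadth of recruitment, not adjustment. Ethnicity, race, insurance and health system are in both models and partly stand in for language. Pattern-mixture analyses already examine departures from MAR. All of this stands and keeps the point minor. It does not explain why sex is absent, since the documents cite no data-quality problem for it. The exploratory heterogeneity analyses name neither variable, so they do not fill the gap.

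A reader might infer that the omission leaves the primary comparison biased. The documents do not support that. Bias in the contrast needs observation to differ by group and by arm, and nothing in them shows such a pattern. Current STOP responders stop receiving messages, but their data are still viewed. Loss of data under the initial opt-out procedure affected a small percentage of early patients. The VA and UCHealth truncations are treated as MCAR.

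A reader might also infer that language is recorded at baseline for everyone and can be added without care. It is documented only where a preference had been stated, and a value updated by text would be a post-randomization variable obtainable only in the texted arms.

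**Conclusion.** The point holds for sex: the list is closed, the variable is available from the EHR, and no reason is given for leaving it out. For language it holds conditionally, for a pre-randomization value of adequate quality. The benefit is a standard error lower by roughly 0.25-1%, assuming the terms explain a further 0.5-2% of PDC variance, and a more plausible MAR assumption, chiefly through the outcome-model term. Even the illustrative month-12 bias of 0.05-0.16 points, which needs an arm-specific pattern that the documents do not show, is small beside a detectable difference of about 2 points and a planning difference of 10; the estimand also combines all twelve months. No conclusion of the trial is likely to depend on it. Severity is minor.

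**What to change.** Before unblinding, amend 3.1.c so that both models include:

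- sex, with its EHR source field named;
- preferred language, if data quality allows, taken only from the EHR value held before randomization and never from a Spanish request made by text, with a category for unspecified preference and a stated rule for VA patients.

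If either is left out, give the reason in one sentence. If unblinding has already happened, keep the primary model as specified and report the extended model as a labelled sensitivity analysis.

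The cost is a line or two of SAP text and a few model terms, with 9,501 patients enrolled. Sex needs no new data collection. Language needs a completeness check and agreed coding at the three systems first.

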- a) If a patient texts "stop" to unsubscribe, the patient is automatically withdrawn from receiving the intervention (messages). Patients may also text misspellings of the word "stop" (such as "tsop," etc.), or send a message indicating the patient would like to be removed from the study. We will continue to view already-collected, standard of care data from these patients.
 - In the initial version of the consent form, we described a "stop" response as a way to "fully withdraw" from the study. These patients were opted out from the study entirely, and data are no longer being collected on these patients. In v.12.3.19 of the info sheet, the language was amended. For patients that have hit "stop" in the original cohort, researchers will call the patients (please find script) to obtain verbal consent to collect their data moving forward. If patients do not consent or cannot be reached after two attempts, we will continue to treat the patients as fully opted out and we will not view their data moving forward. Patients from this original cohort that hit "stop" in the future will be flagged and the calling process will be implemented.
- b) Should a patient respond "done" to indicate they have already filled their prescription or a physician has cancelled their medication, we will stop sending patients any further text messages about refilling the medication in which they had a delay until their medication is again due for a refill (i.e. 30 – 90 days in the future). We will immediately remove the patient from further text messages for this instance of medication nonadherence.
 - Misspellings of "done" or messages indicating they have already filled their prescription or that a physician cancelled their medications will be treated as if they responded "done." If a physician has stopped their medication, we will no longer monitor for medication refills for that specific medication. For other medications, we will resume following the other medication refills. If the patient has a refill gap for the same or for other medications again, we will start delivering text messages within the same arm that they had been previously randomized to.
- c) Patients may request Spanish messages at any time via text. We will start to deliver Spanish language texts following the request. If the patient meets additional criteria for texts during the duration of the study, they will receive Spanish language texts.

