Study description: This individually randomized three-center trial will compare three behavioral nudges based on text and chatbot messaging with usual care to improve adherence to cardiovascular medications.

Setting: The study will be conducted in 17 primary care clinics within 3 health care systems (University of Colorado Health, VA Eastern Colorado Health Care System, and Denver Health Medical Center).

Design: The study will be an individually randomized controlled study with four treatment arms (details of interventions below). Patients become eligible for the study when identified through pharmacy refill data to have a 7-day gap in any prescribed CV medication refills. Eligible patients will be randomized to one of four arms. Randomization will be stratified within each of the clinics, and further stratified within clinics by patients with 1-2 vs 3 or more active CV medication classes at baseline, and using blocks of 4 patients to ensure balance within clinics over time. Thus, within each clinic and number of other medication stratum, each set of 4 consecutively enrolled subjects will be randomized to the four study arms. Treatments will be initiated immediately upon randomization, in response to the 7-day gap.

Intervention: The four treatment arms will be 1) usual care (control); 2) generic text message reminder; 3) text message behavioral nudges only; or 4) text message behavioral nudge plus a pre-programmed AI interactive chat bot designed to identify and resolve barriers to medication refill and adherence.

Delivery of treatments will be as follows:

For patients randomized to one of the three active intervention arms:

- If a patient gaps on a medication at baseline, they receive a text to refill that medication.
 - If a patient gaps on multiple medications at baseline, they receive only one text about all of the medications they gapped on.

- If a patient later gaps on any study medication, they will receive a reminder, regardless of whether they had gapped on or been prescribed the medication at baseline.
- If a patient is removed from a medication, no further texts are sent for that medication. Patients randomized to the control arm receive no texts or other reminders.

2. Study outcomes

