Medications to include in composite PDC: We have considered three ways of selecting medications to include in the primary PDC outcome: PDC1) all medications on which a patient gapped at baseline, PDC2) all medications a patient ever gaps on, calculating PDC from the time of gap, and PDC3) all medications a patient was prescribed at baseline. Medications prescribed after the baseline gap and enrollment will not be included in any of these definitions of PDC, though they will be considered in secondary analyses. Each definition (1-3) has benefits and shortcomings. PDC1 is closest to a pure effect of the intervention, but exploratory analyses of pilot data have shown that many patients who gap in a medication and are randomized also gap in another medication shortly thereafter. Specifically, preliminary data indicate that ~16% of patients gap on an additional medication within 30 days of baseline and ~37% within 90 days. PDC1 will omit these other medications prescribed but not gapped on at baseline. PDC2 provides a similar estimate incorporating these later-gapped medications but excludes medications the patient may never gap on due to reminders for other medications. PDC3 provides an estimate of the overall effect of the interventions on medication patterns, incorporating indirect effects of reminders, but risks inflating PDC and diluting intervention effects by including medications the patient never gaps on. Our primary analyses will use PDC1, while PDC2 and PDC3 will be considered in secondary analyses.

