We will consider several alternate analyses for medication adherence.

Alternate definitions of PDC: Alternate definitions PDC2 and PDC3 and alternate composite PDC-C2 defined above will be analyzed using the same methods as for the primary definition PDC1-C1. These analyses will provide a better understanding of indirect effects of treatments, and of effects of treatments on all medications a patient is prescribed.

Sensitivity to inactive medications: Among medications gapping at baseline, we will repeat the primary analysis limiting our analyses to those medications that had at least one fill during the follow-up period. This will allow us to assess treatment effects among medications that are known to be active, removing medications that were cancelled but not indicated as such by the medical record.

Medication-specific adherence: We will calculate and analyze PDC for each medication individually, to allow analyses of heterogeneity of treatment effect (HTE) by drug class. Multiple comparisons will be adjusted for separately for each analysis using the gatekeeper approach described above.

Medication gaps: We will consider alternate ways of describing medication adherence behavior, including length of initial gap, time to subsequent gap, average length of gaps, and number of 7-day gaps.

3.1.e Secondary examinations of medication adherence

In secondary analyses we will examine several other questions related to medication adherence, including:

Predictors of medication gaps: We will examine predictors of patients having an initial gap of at least 7 days, using the initial pool of candidate patients, to identify types of patients or prescription characteristics for patients at highest risk for non-adherence. We will also examine predictors of subjects having a gap of at least 7 days while enrolled in the study.

Mechanism of treatment effects: We will carry out analyses examining mechanisms or mediators of treatment effect by considering direct responses to reminders, including time from first reminder to refill, and measures of patient engagement, e.g. number of patient text responses to reminders (intensive text and chatbot arms only).

Heterogeneity of treatment effect: We will carry out analyses examining HTE, specifically i) HTE between the three health care systems, and ii) HTE for patient characteristics or subgroups

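### The inactive-medications sensitivity analysis keeps only medications filled after randomisation, so the retained sets are not comparable between arms if the texts change the share ever filled

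*Combined protocol and SAP*

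**What the plan says.** SAP section 3.1.d, under *Sensitivity to inactive medications*, repeats the primary analysis on baseline-gapped medications, "limiting our analyses to those medications that had at least one fill during the follow-up period". Its stated aim is "removing medications that were cancelled but not indicated as such by the medical record". It claims: "This will allow us to assess treatment effects among medications that are known to be active".

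SAP section 1 describes the intervention: "If a patient gaps on a medication at baseline, they receive a text to refill that medication". Treatment starts at randomisation. "Patients randomized to the control arm receive no texts or other reminders". Section 3.1.e lists the time from first reminder to refill among the mechanisms or mediators of treatment effect.

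On cancellations, section 3.1.b says that information "on medication changes and cancellations, will be available from the patient's electronic health record". The protocol section on responding to patients' texts lets a texted patient reply DONE "to indicate they have already filled their prescription or a physician has cancelled their medication".

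**The concern.** The filter selects on a post-randomisation event that the intervention is designed to bring about. A never-filled medication may have been cancelled, or it may be active and simply not taken. The second case is the non-adherence the trial targets, and the filter cannot tell the two apart. If the texts turn some never-filled medications into filled ones, those medications stay in the active arms while their control counterparts are removed. Patients with no refilled baseline-gapped medication leave altogether, although SAP section 3 promises an intention-to-treat analysis of everyone randomised.

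The SAP sees this kind of problem elsewhere. Section 3.1.b faults PDC2 because it "excludes medications the patient may never gap on due to reminders for other medications". Section 3.1.d carries no such caveat. The observation weights and pattern-mixture analyses in 3.1.a and 3.1.b deal with unobserved PDC, not with medications removed by rule.

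What is at stake is how a check on the primary result is read. If the two results disagree, nobody can say whether unrecorded cancellations diluted the primary estimate or selection on the fill distorted the check.

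**Working it through.** The documents give no never-filled share and no PDC by fill status, so the size can only be shown on assumed inputs. The nearest stated figure, 119 per arm in SAP 3.1.f, reproduces (t-test, difference 0.10, SD 0.22, two-sided 0.05/6, 80% power: 118.97), but it does not bear on this point.

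**From the documents.** Enrolment is 1,235 + 7,266 + 1,000 = 9,501 (3.1.f), or about 2,375 per arm. The stage 1 level is 0.05/3 (3.1.a), with two-sided critical value 2.394.

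**Assumed.** One medication per patient. Never-filled shares are n_c (control) and n_a (active). A never-filled gapped medication has PDC 0. PDC is p = 0.70 if filled anyway and q = 0.40, 0.55 or 0.70 if newly filled. The gain among those filling anyway is g.

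**Formulas.**
- All medications: control = (1−n_c)p; active = (1−n_c)(p+g) + (n_c−n_a)q.
- Filled only: divide each by its filled share, 1−n_c or 1−n_a.
- Example (20% vs 15%, g = 0, q = 0.40): 0.80×0.70 = 0.560 against 0.560 + 0.05×0.40 = 0.580. Dividing by 0.80 and 0.85 gives 0.700 against 0.682.
- Reversal stops at g = (n_c−n_a)(p−q)/(1−n_c). For 20% vs 15% that is 0.05×0.30/0.80 = 1.9 points at q = 0.40, 0.9 at q = 0.55 and 0 at q = 0.70.

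Differences in PDC points, for q = 0.40 / 0.55 / 0.70:

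| Never-filled, control vs active | g | All medications | Filled only |
|---|---|---|---|
| 20% vs 15% | 0 | +2.0 / +2.8 / +3.5 | −1.8 / −0.9 / 0.0 |
| 20% vs 15% | 2 | +3.6 / +4.4 / +5.1 | +0.1 / +1.0 / +1.9 |
| 20% vs 15% | 5 | +6.0 / +6.8 / +7.5 | +2.9 / +3.8 / +4.7 |
| 20% vs 18% | 0 | +0.8 / +1.1 / +1.4 | −0.7 / −0.4 / 0.0 |
| 20% vs 18% | 5 | +4.8 / +5.1 / +5.4 | +4.1 / +4.5 / +4.9 |
| 10% vs 8% | 0 | +0.8 / +1.1 / +1.4 | −0.7 / −0.3 / 0.0 |
| 10% vs 8% | 5 | +5.3 / +5.6 / +5.9 | +4.2 / +4.6 / +4.9 |
| 20% vs 20% | 5 | +4.0 | +5.0 |

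In the last row the filter does what the SAP wants: with equal shares it only rescales, 4.0/(1−0.20) = 5.0.

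**Scale, 20% vs 15%, within-filled SD assumed 0.22.** Control SD = √(0.80×(0.22²+0.70²) − 0.56²) = 0.342; active SD is 0.321 to 0.339. With active SD 0.324, the smallest significant difference over all medications is 2.394×√((0.342²+0.324²)/2,375) = 2.3 points (2.3 to 2.4 across cases). With 0.80 and 0.85 of each arm retained it is 1.7 points. The pairs are 2.0–2.1 and 0.9–1.0 at SD 0.12, and 2.6–2.7 and 2.3 at SD 0.30. By normal approximation, with no missing data:
- The +2.0 case is significant over all medications only 37% of the time.
- With g = 2, the chance of significance falls from 90% / 98% / over 99% to 2% / 16% / 61% on restriction.
- With g = 5, it stays at 95% or more at SD 0.22, but is 73% at SD 0.30 with q = 0.40.

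**Alternative: remove an equal cancelled share c.** Take 20% vs 15%, q = 0.40, g = 0, c = 0.15.
- One medication per patient: 0.580/0.85 − 0.560/0.85 = 0.682 − 0.659, or +2.35 points, which is 2.0/0.85. Two medications with independent fill status give the same.
- Suppose instead that half the patients have the same fill status on both medications. In that half, a never-filled control patient leaves only if both are removed (0.75² = 0.5625), so 0.20×0.4375 = 0.0875 stay at zero: 0.56 over 0.8875. The independent half contributes 0.644 over 0.9775. The control mean is (0.56+0.644)/(0.8875+0.9775) = 0.646, and the difference is +3.7 points.

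**The case against.** The strongest reply is that this is one of several alternate analyses, and that the harm is conditional. The primary analysis keeps never-filled medications. A medication drops out only if it has no fill in nominally 365 days, so one late refill keeps it. Candidates also needed a recent fill of a study medication to enter the pool. All of this is true, and it limits the point to this check.

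The 20% scenario may also be too severe. With mean 0.732 and SD 0.22 (SAP 3.1.f) and one medication per patient, a zero-PDC share cannot exceed 0.22²/(0.22²+0.732²) = 8.3%. Dividing by the 75% assumed to gap gives 11%. But that SD is a residual SD for all veterans prescribed the medications, in one of three systems, so it does not bound medications selected for a gap. Even so, the milder rows deserve equal weight. At 20% vs 18% with g = 2, significance falls from 51% / 63% / 74% to 24% / 43% / 64%. At 8% vs 7% it falls from 63% / 70% / 76% to 53% / 63% / 72%. Reversals in the 2-point-imbalance rows (−0.3 to −0.7) are below the restricted threshold of about 1.6 to 1.7 points.

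The planned analysis of initial gap length concerns the same refill, and could hint at an imbalance. It does not correct this comparison, and no by-arm never-filled count is promised.

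Finally, an equal cancelled share is itself untestable, and it would fail if cancellations reported by text counted only in the text arms. That stands as a limit, and it is why one cancellation source must apply to every arm.

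**Conclusion.** The concern holds. The filter conditions on the behaviour the texts request, so it estimates the effect in active medications only if the texts leave the share ever filled unchanged. If that share rises, the restricted result can be pulled towards zero. It reverses only when newly filled medications have lower PDC than those filled anyway and there is little other gain. In the assumed 20% vs 15% case the shift from the all-medications result is 2.8 to 3.8 points. With a 2-point imbalance it is about 0.5 to 1.5 points in the rows shown. Gains of 5 points mostly survive.

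The principle is certain; the size is not, because every fill share and PDC by fill status is assumed. The worry about unrecorded cancellations is legitimate, and the primary result does not depend on this filter.

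**What to change.** In SAP section 3.1.d:

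1. Do not present the fill-restricted result as a robustness check or as the effect in active medications. Label it descriptive and conditional on a post-randomisation fill. Report by arm the number and share of never-filled medications and of patients excluded.
2. For the sensitivity analysis, either define active medications from pre-randomisation orders and fills only, or keep all baseline-gapped medications and vary an assumed unrecorded-cancelled share c, equal in all arms, from 0 to the smallest never-filled share in any arm.
3. State one source for recorded cancellations and apply it identically in every arm. Only texted patients can report a cancellation by reply, and section 3.1.b does not say whether replies supplement the health record.

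The cost is SAP wording, one table by arm and reruns of the primary model on existing data. There are limits. Both c and its equality across arms are assumptions. The 1/(1−c) rescaling is exact only for one medication per patient, and the +2.35 against +3.7 comparison shows that values near the top of the range for c are the least reliable. A pre-randomisation definition will keep some cancelled medications.
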